### **D. DESIGN AND METHODS**

#### **1. Study Design**

We propose a randomized, controlled clinical trial and prospective follow up to evaluate the effect of invasive procedures in the management of PTH. Adolescents and young adults will be recruited from Boston Children's Hospital, Beth Israel Deaconess Medical Center, and Mass General Brigham Pain clinics, Concussion clinics and Headache clinics. Patients will be recruited beginning July 2017.

We propose to study the effect of CMBB versus ONB treatment with lidocaine and steroids. Patient demographics (e.g. age, sex, ethnicity, and race), disease characteristics (e.g. symptoms, duration of the disease, medications taken, etc.), and description of the intervention will be collected. As part of the standard of clinical care at the study sites, patients will complete the intake Standard Pain Questionnaire at baseline. During the first two months of the study, patients will be contacted by our research team via email on a weekly basis requesting them to complete a study questionnaires. After the initial 2 months on the study, we will continue to contact patients every 2 weeks over the next 10-months. Patients will remain in the study up to 12 months after enrollment.

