**Inclusion Criteria:**

- Age 14 – 45 years.
- History of post-traumatic headache or neck pain following a concussion or head injury within the last 2 years.
- Self-reported lack of meaningful benefit with at least one previous treatment trial. Previous treatment could include a migraine prophylactic medication, a neuropathic pain medication, a physical intervention, or a cognitive-behavioral intervention.

**Exclusion Criteria:** Subjects will be excluded in the following circumstances:

- Significant underlying psychological concerns, as determined by study psychologist up on review of standardized assessment
- Lack of parental consent and child assent (if patient age <18 years) or lack of consent (if patient age >18 years). Unable to complete the questionnaire, based on parental or patient estimation of cognitive or language limitations

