**3. Description of Study Treatments or Exposures/Predictors**

Patients enrolled in the study will be randomized to receive either an ONB (Figure 2, additional procedure details provided below) with dexamethasone 2mg each site with 3ml 1% lidocaine, for a total of two sites or a CMBB (Figure 3a & 3b, additional procedure details provided below) with dexamethasone 1.5mg each site with 2 ml 1% lidocaine, for a total of three sites on each side. The assignment of the procedure will be randomized however neither the patients nor the investigator will be blinded to the procedure. If patients exhibit a  $\geq 50\%$  pain reduction on receiving the block evaluated after four weeks, then they may continue to receive blocks as needed, but not more than one every three months. If patients exhibit  $< 50\%$  pain reduction, the patient will be treated as per the clinician's judgment with the possibility of a cross over to the other treatment option in the protocol.

All patients will be followed for 12 months after enrollment and after the crossover of treatments they will continue to be treated and followed per clinical standard of care.

As part of this study, patients will need to complete 8 follow-up visits, of which the first and second will be in-person clinical visits and the other follow-ups could either be conducted in-person at the clinic or via teleconference - video:

a) Visit 1: in-person clinic visit

- At the first visit to the clinic, the physician or nurse will verify the patient's name and date of birth, and will collect information about pain, current and past medicines, and general health. The physician will perform a physical examination and measure heart rate, blood pressure and respiratory rate, and conduct a neurological exam.
- Baseline questionnaires will be taken, including Pain (NRS), Concussion Symptom Score, MIDAS/PedMIDAS, Anxiety, Depression, FDI, and QL.

At the end of the visit, all enrolled patients will be randomized to one of the two minimally invasive procedures, the ONB or the CMBB. Information from the patient's most recent clinical visit note (retrieved from the patient's medical record) may be used to obtain Visit 1 data.

b) Visit 2: Cervical and medial branch block procedures

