The procedure will be performed at Boston Children's Hospital or Beth Israel Deaconess Medical Center or Mass General Brigham Operation Room. Patients may receive sedation as per clinical need, and procedures will be performed in a standardized manner. Neither the patient nor the investigator will be blinded to the type of procedure.

Patients will not be universally sedated however a particular subset of patients may receive sedation. Pediatric patients and some adults with extreme anxiety to procedures will receive mild IV sedation with fentanyl, midazolam and occasionally propofol. This is not general anesthesia but is Monitored Anesthesia Care (MAC). Patients will be awake enough to report any symptoms or discomfort. Anesthesia will be administered either in an Operating Room or Day Surgery Unit setting of the study sites and not in an outpatient setting. A separate anesthesia team consisting of an anesthesiologist and nurse anesthetist (CRNA) will be responsible for administration of anesthesia and airway maintenance. Vital signs will be monitored every 5 minutes and anesthesia adjusted based on patient discomfort.

Details on doses of dexamethasone and lidocaine to be used:

Dexamethasone doses:

Occipital nerve block: 2 mg / block

Cervical facet injections/medial branch block: 1.5 mg / facet joint

Lidocaine doses:

Occipital nerve block: 3 ml of 1% lidocaine / block

Cervical facet injections/medial branch block: 2 ml of 1% lidocaine / facet joint

DESCRIPTION OF OCCIPITAL NERVE BLOCK:

The patient will be in the seated position. The back of the head (occipital area) will be prepped with alcohol pads. Following this, the left or right greater occipital nerve will be accessed at the midpoint of the occipital protuberance and the mastoid process using a 25-gauge 1-1/2 inch needle. 1% lidocaine will be used for skin and subcutaneous analgesia. Following this, area of the left greater occipital nerve will be accessed and the injection fanned. A mixture of 2 mg of dexamethasone and 3 ml of 1% lidocaine will be injected into this area. Following this, the contralateral side will be addressed in a similar fashion (if patient needs bilateral injection). A total of 4 mg of dexamethasone and 6 mL of 1% lidocaine will be injected. The patient will be observed in recovery for complications of bleeding, worsening of symptoms, or paresthesias.

DESCRIPTION OF CERVICAL FACET / MEDIAL BRANCH BLOCK:

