## **I. Data Analysis Plan and Sample Size**

At the time of data analysis, datasets will be downloaded from both REDCap and InForm and merged into Statistical Analysis Systems 9.3 for purposes of analysis. Missing data will be accounted for when the data is coded into respective variables.

In order to detect a 30% difference between treatment groups, and with an  $\alpha$  of 0.05 and  $\beta$  of 0.8, we will need a sample size of 24 subjects per group. Taking into consideration a 30% dropout rate during the study, we estimate a sample size of 63 subjects in the trial.

We will analyze pain scores (NRS), MIDAS/ PedMIDAS, FDI and QL scores as continuous variables. Differences of these parameters from baseline will be the outcomes variables. The differences in pain, functional, and QL scores will first be tested for normality. Assuming normality, T-Tests will be conducted to investigate the differences between the two randomized

groups. If data does not appear to be normal, Wilcoxon Rank Sum Tests will be performed in contrast to T-Tests.

Descriptive statistics will be generated in order to summarize socio-demographic characteristics of study participants. Frequency tables will be generated to describe gender, psychological and pain related comorbidities, history of injury, previous treatment methods and interventions. Similarly, frequency tables will be generated to depict physical exam characteristics, presumed anatomic diagnosis provided by clinicians, and presence of any predictive clinical findings. Continuous characteristics such as age and BMI will be tested for normality using the Shapiro-Wilk test. Continuous characteristics will be summarized using mean and standard deviation if the distribution appears normal, or will be summarized using median and interquartile range if the distribution does not appear normal. We will evaluate baseline differences between responders and non-responders, using chi-square and t-test for categorical and continuous variables, respectively.

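### Three hospital systems recruit and treat, but the plan describes no stratification by site (or any other allocation method) and no analysis includes site, at an avoidable cost in balance and precision

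*Combined protocol and SAP*

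**What the plan says.** Section D.1 recruits from Boston Children's Hospital together with "Beth Israel Deaconess Medical Center, and Mass General Brigham Pain clinics, Concussion clinics and Headache clinics". Section D.3 has all three systems perform the blocks: "The procedure will be performed at Boston Children's Hospital or Beth Israel Deaconess Medical Center or Mass General Brigham Operation Room". The age criterion, "Age 14 – 45 years", applies to the trial as a whole; no age limits are set by site.

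Allocation is covered by two statements in Section D.3. One is that "The assignment of the procedure will be randomized however neither the patients nor the investigator will be blinded to the procedure". The other gives the timing, at Visit 1: "At the end of the visit, all enrolled patients will be randomized to one of the two minimally invasive procedures, the ONB or the CMBB". Neither mentions a ratio, how the sequence is generated, blocks, strata or concealment.

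In Section I, "T-Tests will be conducted to investigate the differences between the two randomized" groups, with a Wilcoxon rank sum test if the data are not normal. Repeated-measures and multiple regression analyses follow. The regression takes treatment and epidemiological, clinical and psychosocial characteristics as independent variables. The list under Other Independent Variables in Section E has age, BMI, sex, examination findings, comorbidities and diagnosis. Site appears in none of these.

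**The concern.** Site could plausibly be prognostic here, on the plan's own terms. A children's hospital probably enrols younger patients than the other two systems. That is an inference, but a fair one. Aim 4 expects younger age to go with better response, and several instruments have separate adult and paediatric versions.

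If allocation is not balanced within site, chance can give one site more of one procedure, and part of any site difference then enters the observed treatment difference. If site is also left out of the analysis, between-site variance stays in the error term. With 63 patients over three sites, both effects are large enough to measure and cheap to remove. The trial is open, so the missing description of concealment matters as well: nothing shows that the next assignment is hidden from the person enrolling.

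**Working it through.** **1. The plan's own figures (Section I).** 24 per group gives 48, and 48 × 1.3 = 62.4, rounded up to the stated 63. The plan gives no SD. With two-sided α 0.05 and 80% power (the plan does not state sidedness), n per group = 2(1.96 + 0.84)²/d², so 24 per group corresponds to d of about 0.81 SD. That is the treatment effect used below. I show 48 patients as well as 63, because 48 is the evaluable number the plan is built on.

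**2. How often sites split unevenly.** Site sizes are assumed. The table gives the chance that at least one site splits 2:1 or worse.

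| Allocation | Sites 21/21/21 | Sites 33/20/10 |
|---|---|---|
| Fixed 32:31 total, no strata | 0.246 | 0.338 |
| Simple coin toss | 0.47 | about 0.47 |

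For the coin toss with equal sites, one site of 21 splits 14:7 or worse with probability 0.189, and 1 − (1 − 0.189)³ = 0.47. With a fixed total and unequal sites, the site of 10 drives the result: it alone reaches 2:1 with probability 0.30, against 0.012 for the site of 33. The frequency of splits therefore overstates the harm, and the shift in the treatment difference is the better measure.

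**3. How far the estimate moves.** The simulation used 6,000 runs per scenario, three sites of 21, within-site SD 1 and simple randomisation. With site means at −0.5, 0 and +0.5 SD (assumed), the shift has mean zero, an average absolute size of 0.09 SD and a 95th percentile of 0.20 SD. Against 0.81 SD, that 95th percentile is 0.20/0.81, about 25% of the effect.

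**4. False positives.** Under simple randomisation the unadjusted t-test rejected a true null in 0.045 to 0.053 of runs across all scenarios.

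**5. Power at 0.81 SD, equal sites.**

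| Site means (SD), assumed | N | Simple, unadjusted | Stratified and adjusted | Gain |
|---|---|---|---|---|
| 0, 0, 0 | 63 | 0.88 | 0.89 | 1 point |
| 0, 0, 0 | 48 | 0.78 | 0.78 | none |
| 0, 0, +0.5 | 63 | 0.867 | 0.892 | 3 points |
| 0, 0, +0.5 | 48 | 0.752 | 0.778 | 3 points |
| −0.5, 0, +0.5 | 63 | 0.83 | 0.88 | 5 points |
| −0.5, 0, +0.5 | 48 | 0.71 | 0.78 | 7 points |
| +1, 0, 0 | 63 | 0.81 | 0.88 | 7 points |
| +1, 0, 0 | 48 | 0.69 | 0.77 | 8 points |

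With unequal sites of 37/13/13 and N = 63, the −0.5, 0, +0.5 pattern gives 0.83 against 0.89. If the largest site lies 1 SD apart, the result is 0.79 against 0.88, a gain of 9 points.

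**6. Hand check of the −0.5, 0, +0.5 row at N = 63.** The between-site variance is (0.25 + 0 + 0.25)/3 = 0.167, so the total is 1.167. The standardised effect is 0.81 × √(63/4) = 3.21 with site removed and 3.21/√1.167 = 2.98 with it left in. Normal-approximation power is Φ(3.21 − 1.96) = 0.90 against Φ(2.98 − 1.96) = 0.85, the same 5-point gap.

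**7. Interval width.** A site term narrows the interval by 1 − √(1 − share of variance due to site). A share of 5% gives 2.5% and a share of 20% gives 10.6%. The pattern in step 6 has a share of 0.167/1.167 = 14%, which gives about 7%.

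**8. Stratifying without adjusting.** The t-test then becomes conservative: type I error was 0.036 for site means at −0.5, 0, +0.5 and about 0.030 with one site 1 SD apart. The two changes belong together.

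**The case against.** A reader might infer more than the documents support, in four ways.

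- *That the plan opts for unstratified randomisation.* It does not say so. It is silent on the method altogether, which neither confirms nor excludes stratification.
- *That sedation practice and operators differ by site.* Section D.3 sets one sedation rule, tied to the patient: "Pediatric patients and some adults with extreme anxiety to procedures will receive mild IV sedation with fentanyl, midazolam and occasionally propofol". It also states that "Patients may receive sedation as per clinical need, and procedures will be performed in a standardized manner", with one technique described for each block. Nothing is said about operators by site.
- *That a site difference could pass for a treatment effect.* Randomisation prevents this on average. Mean bias was about zero, and the ordinary standard error already allows for chance imbalance, as step 4 shows.
- *That the open label creates site confounding.* It does not. It bears only on concealment.

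It can also be said that age, the most likely route for a site effect, is a listed covariate and could enter the planned regression. That is so, but the regression is not the stated between-arm test, and age need not capture everything that differs between sites. The strongest remaining objection is size: the gain is modest and rests on assumed site effects. That stands. It limits how serious the point is, but it does not argue for leaving the method unspecified, because the remedy loses nothing measurable when sites are alike.

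**Conclusion.** The point holds as one about design efficiency and specification. The plan describes no allocation method and no stratification by site, and its between-arm test and listed covariates leave site out. The type I error rate is not threatened. The cost is avoidable chance imbalance, with a shift of up to about 0.20 SD at the 95th percentile, and about 3 to 8 points of power in the equal-site scenarios, from one site 0.5 SD apart to one site 1 SD apart. It is about none if sites do not differ. These sizes rest on assumed site numbers, assumed site means and the 0.81 SD effect implied by 24 per group; the documents give none of the three. The change is worth making because it is cheap, not because the trial would otherwise be invalid.

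**What to change.** In Section D.3, state that patients are randomised 1:1 in permuted blocks of varying size, stratified by site, with the allocation released centrally after eligibility and baseline scores are recorded. The REDCap system already in use is one possible route.

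In Section I, include site in the between-arm comparison: as a fixed effect in a linear model in place of the t-test, or through a van Elteren test stratified by site if the Wilcoxon route is taken.

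If enrolment has begun, the site term can still be prespecified before analysis. In the −0.5, 0, +0.5 scenario, adjustment after simple randomisation gives power of 0.87 at N = 63 (0.83 unadjusted) and 0.76 at 48 (0.71 unadjusted). If sites do not differ, adjustment alone costs about 1 to 2 points (0.88 to 0.87, and 0.78 to 0.76).

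The cost of the full change is a stratified list, one model term with two degrees of freedom, and a small possible arm imbalance if a site enrols very few patients. Sample size, visits and treatments are unchanged.

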**Protocol Title: A Prospective Controlled Treatment Trial for Post-Traumatic Headaches**

**NCT#: 03007420**

**Principal Investigator: [name]**

**A. SPECIFIC AIMS AND HYPOTHESIS**

**1. To compare the efficacy of Occipital Nerve Blocks (ONB) vs. Cervical Medial Branch Blocks (CMBB) in patients presenting with post-traumatic headache (PTH) who were non-responsive to previous interventional management.**

- To examine differences in Numeric Rating Scale (NRS) pain measurements (> 50% or < 50% pain reduction)
- To examine differences in Migraine Disability Assessment (MIDAS) and Pediatric Migraine Disability Assessment (PedMIDAS) scores
- To describe differences in functional outcomes using the Functional Disability Inventory (FDI) and the Pain Disability Index (PDI).
- To study differences in Quality of Life (QL) and Pediatric Quality of Life (PedsQL) scores

**Hypothesis:** Treatment with CMBB with steroids and lidocaine will be associated with a greater improvement in pain scores, functional and QL scores than the ONB.

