#### **E. Definition of Primary and Secondary Outcomes / Endpoints:**

##### **Primary Outcome Measures**

The overall goal of this study is to examine the change in PTH and / or axial neck pain in groups of patients receiving minimally invasive nerve block interventions (ONB with lidocaine and steroids vs. CMBB with lidocaine and steroids). The primary outcome is defined as change in pain

intensity scores (NRS), which will be collected at baseline, weekly for two months, and then bi-weekly throughout rest of the study.

Pain scales: The numerical rating scale (NRS) will be utilized in this study. Patients will rate their pain score on a scale of 0 to 10 with 0 being no pain and 10 being the worst pain imaginable.

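### The primary NRS comparison has no named analysis time point and no rule for scores after crossover, so the 12-month between-group analysis compares starting strategies rather than ONB with CMBB

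*Combined protocol and SAP*

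**What the plan says.** Aim 1 (section A) compares the two blocks, and its hypothesis is that "Treatment with CMBB with steroids and lidocaine will be associated with a greater improvement in pain scores, functional and QL scores than the ONB". The same aim frames pain as a split at 50%: "To examine differences in Numeric Rating Scale (NRS) pain measurements (> 50% or < 50% pain reduction", with no date attached.

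Section E defines the primary outcome as the change in "intensity scores (NRS), which will be collected at baseline, weekly for two months, and then bi-weekly throughout rest of the study". That is a collection schedule, not an analysis time.

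Section I makes the difference from baseline the outcome variable. It compares the two randomised groups by t-test or Wilcoxon rank sum test and adds a repeated-measures analysis over time. The sample-size sentence begins "In order to detect a 30% difference between treatment groups" and gives neither a time nor a scale. Section I also mentions an exploratory analysis meant to suggest how treatments might be sequenced.

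Section D.3 contains the only dated response, "pain reduction on receiving the block evaluated after four weeks", and uses it to decide further treatment. Patients at or above 50% reduction may go on with blocks ("they may continue to receive blocks as needed, but not more than one every three months"). Those below 50% are managed at the clinician's judgment, "with the possibility of a cross over to the other treatment option in the protocol". The section also states that "neither the patients nor the investigator will be blinded to the procedure". Everyone is followed to 12 months after enrollment, including after crossover.

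**The concern.** Two things are left open: when the primary comparison is made, and which scores enter it once a patient has received the other arm's block.

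The second matters because patients become eligible to cross through poor response to the first block. From then on, a score in the ONB arm may reflect ONB followed by CMBB, and the reverse in the CMBB arm. A 12-month comparison as randomised therefore describes a policy of starting with one block and possibly switching. That is a legitimate question, but it is not the one in Aim 1, and the plan treats sequencing only as exploratory.

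The first matters because the outcome is patient-reported and unblinded, and the group size is 24. With no time fixed in advance, the headline result could be settled after the data are seen.

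**Working it through.** **1. Where a time point could be stated**

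| Place | What it gives | Analysis time? |
|---|---|---|
| Section A, Aim 1 | 50% responder split | none |
| Section D.3 | evaluation four weeks after the block | a treatment decision |
| Table 1 | a 1-month evaluation row | a survey date |
| Section E | change in NRS and its schedule | none |
| Section I, sample size | a 30% difference | none |
| Section I, tests | difference from baseline, randomised groups | none |
| Section I, repeated measures | over time | no window or contrast |

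Four weeks is at most implied, by section D.3 and the 1-month row.

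**2. Survey count (Table 1 rows that include the pain assessment)**

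- Up to the 1-month evaluation: weeks 1, 2, 3 and 1 month = 4.
- After it: weeks 5, 6, 7 and 2 months (4); week 10 and 3 months (2); weeks 14 to 22 and 6 months (6); weeks 26 to 34 and 9 months (6); weeks 38 to 46 and 12 months (6). 4 + 2 + 6 + 6 + 6 = 24.
- Total 4 + 24 = 28, and 24/28 = 86%.

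Section D.3 times the response evaluation from the block, but times Visits 3 to 8 from enrollment. If Table 1 also runs from enrollment and the block comes d weeks later (d is an assumption), the surveys later than week 4 + d number 24, 23, 22, 21 and 20 for d = 0 to 4. Months 1, 2 and 3 are taken as weeks 4, 8 and 12.

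**3. Effect of crossover on the later contrast (illustration)**

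The documents give no crossover rate, NRS mean or SD. Assumed inputs: baseline NRS 6; mean reduction 2 (ONB) and 3 (CMBB); SD 2.5; scores kept within 0 to 10. Bounding turns the nominal 1-point difference into 0.91.

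- Share below 50% reduction (a reduction under 3 points): ONB Φ((3 − 2)/2.5) = Φ(0.4) = 66%; CMBB Φ((3 − 3)/2.5) = Φ(0) = 50%.
- A stated fraction of these patients crosses. The later score reflects either the second block alone or the better of the two responses. The correlation between a patient's two responses is 0 to 0.8.
- Simulated with 2,000,000 patients per arm; the ranges below hold to about 0.01.

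| Share of <50% responders crossing (ONB / CMBB) | Later difference, points |
|---|---|
| none | 0.91 |
| 25% / 25% | 0.63 to 0.73 |
| 50% / 50% | 0.35 to 0.53 |
| 50% / 25% | 0.27 to 0.49 |
| 25% / 50% | 0.56 to 0.90 |

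The 50% / 50% row, at correlation 0, 0.5 and 0.8, is 0.41, 0.37 and 0.35 with the second block alone, and 0.47, 0.50 and 0.53 with the better response kept. The sample-size multiplier for equal power is the squared ratio of standardised differences. On raw differences it is (0.91/0.53)² = 2.9 to (0.91/0.35)² = 6.8; allowing for the changed SD, it is 2.7 to 7.1.

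**4. Ceiling on the cost of a free time point**

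Assume no true difference, 24 per group, a two-sided t-test at 0.05 at each of the six visits (1, 2, 3, 6, 9 and 12 months), equal between-visit correlation, and any significant result reported. The chance of at least one is about 21, 17, 14 and 11% at correlations 0.5, 0.7, 0.8 and 0.9.

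**The case against.** The plan is not silent on grouping: section I says the randomised groups are compared. It assigns data over time to a repeated-measures analysis, and its exploratory sentence shows that treatment sequences were considered. Aim 1's 50% split, the four-week evaluation and the 1-month row all point the same way. This stands in part. Grouping as randomised is indicated, but which scores enter is not, and an implied time does not bind the analyst.

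The illustration can be challenged too. Crossover is only a possibility, every rate is assumed, and the model has no waning of either block. Its standardised difference is about 0.4, whereas 24 per group at 80% power needs about 0.83. That is fair, so the point figures should not be read as forecasts. Two further settings (reductions 2 vs 3.8 with SD 2.5, and 1.5 vs 2.5 with SD 2.0) gave the same pattern: over all three, equal 50% crossover kept 32 to 59% of the difference and equal 25% kept 66 to 79%. Dilution is not universal, however. At 25% ONB / 50% CMBB the difference can stay at 0.90 of 0.91, with a sample-size multiplier of 0.93.

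A longer horizon is also defensible, since section B stresses sustained relief. That supports keeping the 12-month analysis, under a name that says what it estimates.

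A reader might infer that the as-randomised 12-month comparison is invalid. It is not: randomisation protects it, and only its label and question are at issue. Nor do repeat blocks of the assigned type mix the arms, so they are not part of this point.

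**Conclusion.** The concern holds for the readable text, with the reservation that Figure 1 is not shown. No primary analysis time is named, no rule covers NRS scores after crossover, and up to 24 of 28 post-baseline surveys are affected (20 to 24 if Table 1 runs from enrollment and the block follows within four weeks). These findings rest on the documents alone. This should be fixed before analysis, because as written the 12-month between-group result answers a different question from Aim 1.

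The size of the effect is conditional on the inputs in step 3. Equal crossover of a quarter to a half leaves roughly 0.35 to 0.73 of 0.91 points; unequal crossover ranges from a larger loss to almost none.

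Two stronger readings are not supported. One is that crossover would reverse the result: none of the scenarios above does so, and the documents give no rates that would justify more extreme ones. The other is that the trial's error rate is 11 to 21%: that is a ceiling for picking any significant visit, a procedure the plan nowhere states.

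**What to change.** 1. Name one primary endpoint: NRS change from baseline at the four-week evaluation of the first block, analysed as randomised, using a score recorded before any further procedure. Report the 50% responder measure from Aim 1 at the same time as supporting.
2. Keep the 12-month repeated-measures analysis as randomised, but label it a comparison of ONB-first and CMBB-first strategies. Report crossovers by arm, separately from repeat blocks.
3. State whether Table 1 weeks run from the block or from enrollment. Section D.3 counts the response evaluation from the block, and the side-effect items that start at Week 1 suggest the same; the visit schedule in D.3(c) counts from enrollment. If from enrollment, use the existing survey nearest four weeks after the block, take the earlier one in a tie, and never use one after a further procedure.

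**Cost.** If the weeks run from the block, only wording changes. If from enrollment, no new survey is needed. Blocks 1, 2, 3 or 4 weeks after enrollment match the week 5, 6, 7 and 2-month surveys exactly. For delays of 5 to 8 weeks a survey falls within one week of the target. The ties are at 5 weeks (target week 9, between weeks 8 and 10) and 7 weeks (target week 11, between weeks 10 and 12). The block date must be in the dataset. The week 5 to 7 surveys do not ask about additional procedures, so those dates must come from the medical record, which section G already uses. No treatment rule changes.

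**Downside.** The head-to-head claim covers about one month, and sustained relief is answered only as a comparison of starting strategies.

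The mismatch between D.3(d) and Table 1 on when MIDAS and quality of life are repeated is a separate minor point.
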